17.6 Stopping the trial

The trial will stop for safety if there is sufficient evidence that the lowest dose is too toxic (if P(T>0.48 | dose = 1, current data) > 0.7).

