2.2 Objectives

The table below shows the full list of trial objectives and corresponding outcome measures. Objectives in grey will be not analysed by trial statisticians within CSM so are not covered by this SAP.

Primary Objective	Endpoints/ Outcome measures	Time point(s) of evaluation of this end point	Analysis population
To determine the maximum tolerated dose (MTD), and therefore recommended phase II dose (RPTD), of atovaquone when combined with radical concurrent chemoradiotherapy in patients with non-small cell lung cancer (NSCLC)	The dose of atovaquone associated with no more than 48% dose limiting toxicity (DLT) rate (target toxicity level)	From week -2/-3 until three months post-completion of CRT	All patients who have received at least one dose of atovaquone
Secondary Objectives			
To assess the safety and	Adverse events graded per	From screening/baseline until	All patients who have
toxicity profile of atovaquone	Common Terminology	six months post completion of	received at least one dose of
in combination with radical	Criteria for Adverse Events	CRT	atovaquone

concurrent chemotherapy for	(CTCAE) v4.03		
NSCLC	. ,		
To confirm feasibility of measuring hypoxia metagene signature using 3'RNA-Seq in diagnostic NSCLC samples	Hypoxia metagene signature from diagnostic tissue using 3'RNA-Seq	At baseline	
To assess pre-treatment agreement of: 1. FMISO PET-CT with plasma miR-210 level 2. FMISO PET-CT with tumour hypoxia gene expression	 Tumour hypoxic volume determined by FMISO PET-CT Plasma miR-210 level Hypoxia metagene signature from diagnostic tissue using 3'RNA-Seq 	Week -2/-3 (prior to atovaquone treatment)	 All patients with outcome measures from both the baseline FMISO PET-CT scan and the baseline blood sample
To assess agreement in changes in FMISO PET-CT and plasma miR-210 level following two weeks (+/- 7 days) of atovaquone	 Tumour hypoxic volume determined by FMISO PET-CT Plasma miR-210 level 	 Week -2/-3 (prior to atovaquone treatment) Following two weeks (+/- 7 days) of atovaquone treatment 	All patients with outcome measures from FMISO PET-CT scans and blood samples taken at both time points
To assess the tumour response rate at three months following treatment	Response to treatment assessed per Response Evaluation Criteria in Solid Tumours (RECIST) V1.1	Three months post completion of CRT	All patients who commence chemoradiotherapy treatment within the study
Exploratory Objectives			

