Additionally, since the window to observe toxicities is long, the TMG may opt to pause recruitment whilst on-trial patients complete their treatment. The trial will stop for safety (i.e. before reaching the maximum number of patients specified by the sample size) if there is sufficient evidence to suggest that the lowest dose is too toxic. More specifically, we will consider dose level 1 (450mg) to be too toxic if, given all the available data, there is more than 70% probability that the DLT rate is greater than the target toxicity level of 48%.

The SRC Charter document for this trial will define the exact membership and who should be present for decisions to be made. Further internal or external experts may be consulted by the SRC, as necessary. Any PI can request an ad hoc SRC meeting at any time in order to facilitate the immediate communication of any emerging safety issues during the course of the trial.

The Independent Radiotherapy and Imaging Oversight Committee (RIOC) will act as the Trial Steering Committee (TSC). The role of RIOC is to provide oversight for the trial on behalf of the Sponsor and Funders. RIOC will provide overall supervision of the safe and effective conduct of the trial, as further defined in the RIOC charter. At least annually, RIOC will review trial progress against agreed milestones, adherence to protocol, and patient safety, and consider new information. RIOC has the authority to recommend study closure where appropriate. Membership of RIOC includes PPI representation.

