6. ANALYSIS

6.1 Outcome Definitions

Primary outcome

To determine the maximum tolerated dose (MTD), and therefore recommended phase II dose (RPTD), of atovaquone when combined with radical concurrent chemoradiotherapy

The outcome is the occurrence (yes/no) of a DLT within the DLT assessment period. For patients without a DLT, time observed within the DLT assessment period will also be taken into account in the analysis. The total i.e. maximum duration of the DLT assessment period for each patient is the length of the atovaquone run-in period (1-3 weeks) which will be pre-specified before the patient starts treatment, plus the length of CRT treatment (6.5 weeks= 45 days) plus follow-up duration (12 weeks = 84 days). At final analysis, patients without a DLT will have completed the DLT period unless they withdrew early. The MTD will be the dose level with posterior mean DLT rate closest to the target toxicity level of 48% when the dose-toxicity model is updated for the final analysis.

For the definition of a DLT, see Appendix 4.

Secondary outcomes

To assess the safety and toxicity profile of atovaquone in combination with radical concurrent chemotherapy

Adverse events from the first dose of atovaquone to six months post completion of CRT will be presented (see Appendix 3).

To confirm feasibility of measuring hypoxia metagene signature using 3'RNA-Seq in diagnostic NSCLC samples

To assess agreement of FMISO PET-CT with plasma miR-210 level and tumour hypoxia gene expression pretreatment with atovaquone

Hypoxia assessed using the baseline FMISO PET-CT scan will be measured using tumour to blood ratio (TBRvolume) (ml).

Plasma miR-210 level will be derived from the baseline blood sample.

Baseline is at week -2/-3 prior to receiving the first dose of atovaquone.

To assess agreement in changes in FMISO PET-CT and plasma miR-210 level following two weeks (+/- 7 days) of atovaquone

Change in FMISO PET-CT will be the % change between TBRvolume (ml) derived from the baseline and pre-CRT scans.

Change in plasma miR-210 level will be the % change between miR-210 level derived from the baseline and pre-CRT blood samples.

Baseline is at week -2/-3 prior to receiving the first dose of atovaquone and pre-CRT is at week -1 (two weeks (+/- 7 days) after starting atovaquone and prior to receiving any CRT.

To assess the tumour response rate at three months following treatment

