6.2 Analysis Methods

Primary analysis

To determine the maximum tolerated dose (MTD), and therefore recommended phase II dose (RPTD), of atovaquone when combined with radical concurrent chemoradiotherapy

All trial patients who received at least one dose of atovaquone will be included in the primary analysis. The same analysis is used during dose escalation as for the final analysis.

The analysis will follow the TiTE-CRM. A two-parameter logistic model will be used to model the relationship between dose and toxicity i.e. the dose toxicity curve (DTC). Dose recommendations following the first two evaluable patients will be made using all current toxicity data as follows:

- Data for patients who have completed the DLT assessment period or experienced a DLT will contribute full information to this model.
- Data for patients who have not completed the DLT assessment period will contribute partial information to the model, weighted proportionally to the observed portion of their time window, and treating them as not experiencing a dose limiting toxicity. The weight function is defined in the equation below as w_i.

There are 4 atovaquone doses which are coded x = 1:4. Assuming dose 1 is the reference dose, d^* , we have treated J patients with dose x_j , j = 1, ..., J, then we model the probability of a DLT occurring using the weighted likelihood given by

$$L(\theta) = \prod_{j=1}^{J} \left[\theta_{x_j} * w_j \right]^{y_j} \left[(1 - \theta_{x_j}) * w_j \right]^{1 - y_j}$$

where

 $y_{j} = \begin{cases} 1 \text{ if dlt occured} \\ 0 \text{ if no DLT} \end{cases}$ $g\left(\theta_{x_{j}}\right) = logit\left(\theta_{x_{j}}\right) = log(\alpha) + \beta log\left(\frac{x_{j}}{d^{*}}\right) \text{ this is the unweighted two-parameter logistic model}$ $w_{j} = \begin{cases} 1 \text{ if } y_{j} = 1 \\ \min\left(1, \frac{u_{j}}{T_{i}}\right) \text{ if } y_{j} = 0 \end{cases}$

 u_j = time patient j has been followed for and T_j = total DLT window for patient j = pre-specified run-in time + 45 days + 84 days (note: as patients are followed up in the trial beyond the DLT observation period, u_j can exceed T_j in which case the weight for patient j in the model will still be 1).

Further detail on the chosen prior distributions for the parameters and simulation results is described in Appendix 1.

See Neuenschwander, Branson and Gsponer (2008) and Cheung YK and Chappell R (2000) for descriptions of the model

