SAP Version No: V1.0 Date: 17Jun2021 SAP Author: [name] OCTRU-OST-001_V3.0_16Feb2018 Effective Date 23Feb2018

Dose-escalation rules

At each analysis the dose recommended by the toxicity model will be the dose with posterior mean DLT rate closest to the target toxicity level of 48%, subject to no dose skipping. However in order to escalate to the next dose, there must also be at least one patient on the previous highest dose fulfilling the following criteria:

- Completed ≥1 full cycle of CRT (i.e. at least three weeks of RT)
- Received ≥50% the specified dose of cisplatin
- Taken ≥75% their allocated dose of atovaquone
- Not experienced a DLT

There is no restriction on dose de-escalation.

Early stopping

At each analysis, the TMG will be recommended to stop the trial early for safety if there is greater than 70% probability that the DLT rate at the lowest dose (dose 1) exceeds the target toxicity level of 48% i.e. if P(risk of DLT>0.48 | dose = 1, current data) > 0.7, which would suggest the lowest dose is too toxic.

Definition of MTD

The MTD will be the final recommended dose after the trial has completed recruitment and all participants had completed the DLT window (or had a DLT/withdrawn) using all data accumulated in the trial. The MTD will constitute the RPTD.

If the trial stops early for toxicity, the MTD will be assumed to be lower than dose 1 and the RPTD will not be established.

Secondary and tertiary analyses

There will be no formal analysis of the secondary or tertiary objectives. See template in Appendix 3 for tables and figures that will be presented.

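### The too-toxic criterion for dose 1 reaches the reported MTD only through an early stop, so the reported MTD can contradict the complete data

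*SAP*

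**What the plan says.** **Criterion.** Protocol 17.6 stops the trial for safety "if P(T>0.48 | dose = 1, current data) > 0.7". SAP 6.2 gives the same threshold as a recommendation: "At each analysis, the TMG will be recommended to stop the trial early for safety if there is greater than 70% probability". SAP 3.4 places the stop in time: "The trial will stop for safety (i.e. before reaching the maximum number of patients specified by the sample size").

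**Data used.** SAP 3.4 runs an analysis at every enrolment. A DLT counts in full. Under SAP 6.2, patients still inside the window are "weighted proportionally to the observed portion of their time window, and treating them as not experiencing a dose limiting toxicity".

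**Conclusion after a stop.** SAP 6.2, Definition of MTD, says that after an early stop for toxicity "the MTD will be assumed to be lower than dose 1 and the RPTD will not be established".

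**Conclusion otherwise.** SAP 6.1: "The MTD will be the dose level with posterior mean DLT rate closest to the target toxicity level of 48" per cent at the final model update. Protocol 17.5 and SAP 6.2 likewise take the final recommended dose as MTD, and the MTD becomes the RPTD. SAP 6.1 has no exception for a trial that stopped early. The endpoint in SAP 2.2 is "The dose of atovaquone associated with no more than 48% dose limiting toxicity (DLT) rate (target toxicity level").

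**Final analysis.** SAP 3.5 schedules it after the six-month visit or withdrawal of every enrolled patient. SAP 6.2 says the method is the one used during escalation.

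**The concern.** One probability defines dose 1 as too toxic, but it changes the reported result only if it crosses 0.7 while patients are still being enrolled. Nothing says what to report when the probability on complete windows disagrees with what happened at the interims.

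- **(a) No stop, but complete data exceed 0.7.** The closest-to-48% rule can only return one of the four doses. Protocol 17.1 assumes that toxicity rises with dose. So once the dose-1 posterior mean is above 48%, every higher dose is further away and dose 1 is named.
- **(b) Stop, but complete data do not exceed 0.7.** SAP 6.2 has already fixed the label as below dose 1, while SAP 6.1 read alone would name a dose.

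At stake is the primary conclusion. The trial could recommend a dose that its own criterion calls too toxic, or report the lowest dose as above the MTD against its own completed follow-up.

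**Working it through.** **Inputs from the documents.** Target 0.48 and threshold 0.7 (SAP 6.2). N = 20 (SAP 3.3). Window = run-in of 7 to 21 days + 45 + 84 = 136 to 150 days (SAP 6.1). Accrual one patient per month (Protocol 17.4). About four to five patients are therefore inside the window at any look.

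**Assumptions.** The priors are in SAP Appendix 1, which was not supplied, so there is no stated operating characteristic to reproduce. I used a dose-1-only model (all patients on dose 1) and eight priors: uniform on the rate θ, and seven normal priors on its log-odds.

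**Formula.** With y DLTs and weights w_j for the DLT-free patients, the posterior is proportional to prior(θ) × θ^y × Π(1 − w_j θ), and P = Pr(θ > 0.48). This is the standard TITE weighting.

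**(a) Late DLTs.** Suppose no earlier look has fired. When patient 20 registers there are 9 DLTs in 19. Of the 10 DLT-free patients, four are pending. At 30.4-day spacing in a 143-day window their weights are 0.85, 0.64, 0.43 and 0.21. Three late DLTs among those four and patient 20 give 12 in 20. With the uniform prior and full weights, 9/19 gives Beta(10, 11) and P = 0.483. Then 12/20 gives Beta(13, 9), P = 0.855 and mean 13/22 = 0.591.

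**(b) Pending patients who finish DLT-free.** Three DLTs, plus four pending at weights 0.7, 0.5, 0.3 and 0.1. If all four complete without a DLT, the uniform prior gives Beta(4, 5) and P = 0.408.

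| Prior on dose-1 rate | 9/19, full weights | 9/19, four pending | 12/20 | Mean at 12/20 | 3 DLTs, 4 pending | 3/7 complete |
|---|---|---|---|---|---|---|
| Uniform | 0.483 | 0.697 | 0.855 | 0.591 | 0.864 | 0.408 |
| Median 0.30, SD 1 | 0.352 | 0.547 | 0.749 | 0.548 | 0.584 | 0.241 |
| Median 0.30, SD 2 | 0.441 | 0.662 | 0.836 | 0.585 | 0.830 | 0.338 |
| Median 0.40, SD 1.5 | 0.451 | 0.666 | 0.836 | 0.583 | 0.810 | 0.359 |
| Median 0.48, SD 2 | 0.476 | 0.696 | 0.856 | 0.594 | 0.881 | 0.392 |
| Log-odds mean −1, SD 1 | 0.328 | 0.519 | 0.729 | 0.541 | 0.539 | 0.212 |
| Log-odds mean −1, SD 1.5 | 0.404 | 0.618 | 0.806 | 0.571 | 0.732 | 0.292 |
| Log-odds mean −0.5, SD 2 | 0.457 | 0.677 | 0.845 | 0.589 | 0.854 | 0.362 |

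Contradiction (a) appears under all eight priors. Contradiction (b) appears under six. Under the two priors with SD 1 the trial does not stop in this example.

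**The printed likelihood.** SAP 6.2 prints the DLT-free term as (1 − θ) multiplied by w. Taken literally, w is a constant and cancels, so pending patients count as full non-DLTs. P can then only rise as follow-up completes. Contradiction (b) cannot occur, and (a) becomes more frequent.

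**Frequency, as an illustration only.** The full two-parameter design was simulated 400 times per setting under the first four normal priors in the table, with uniform DLT times, a 143-day window and no TMG override.
- (a) occurred in 0 to 6% of all trials with standard weights, and in 0 to 15% with the printed likelihood. Among trials that did not stop, with standard weights, it was 3 to 6% at a true dose-1 rate of 0.48 and about 13 to 38% at 0.60 to 0.70. Dose 1 was named every time.
- (b) affected 16 to 68% of early stops with standard weights, 11 to 61% with power weights (1 − θ)^w, and none with the printed likelihood.

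**The case against.** A reader might infer that the model is never refitted after a stop. The documents do not support that. SAP 3.5 schedules a final analysis with no exception for a stopped trial, SAP 6.1 speaks of updating the model for it, and SAP 6.2 applies the criterion at each analysis. What is missing is a conclusion attached to that fit.

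A reader might also take the simulated share of stops as the error rate of this trial. It is not. Protocol 17.2 says the priors are calibrated for sensible early recommendations. Under the tightest simulated prior (median 0.30, SD 1), tying the label to complete data moves the share of trials reporting below dose 1 only from 5 to 3%, 28 to 24% and 61 to 54% at true rates of 0.30, 0.48 and 0.60. The large shifts come from vague priors.

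Other points carry weight. SAP 6.2 only recommends a stop to the TMG, whereas SAP 3.4 and Protocol 17.6 say the trial will stop; those passages must be reconciled. The TMG may pause recruitment, and Protocol 23.5 allows re-opening after a halt. In case (b) no RPTD results either way, so only the label changes.

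None of this supplies the missing rule. A pause is optional. The toxic-scenario sensitivity analysis in SAP 6.4 runs only at interims and only assumes extra DLTs. The other sensitivity analysis restricts patients by atovaquone received. Neither alters the reported MTD, and none of these points touches case (a).

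**Conclusion.** The concern holds as a gap in the reporting rule. The too-toxic criterion has no role in the final conclusion unless it fired before full recruitment.

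Case (a) is the firmer half. It follows from the stated rules, does not need the weighting to work in any particular way, and conflicts with both the plan's own criterion and the endpoint's ceiling of 48%. In the example it appears under every prior tried. It is uncommon overall.

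Case (b) is conditional. It is small under tight priors, larger under vague ones, and absent if the printed likelihood is taken literally. The text of SAP 6.2 and the method it cites suggest that real partial weighting was intended.

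All frequencies rest on assumed priors, DLT timing and accrual, and cannot be firmed up without Appendix 1. Nothing here suggests that stopping recruitment on interim safety data is wrong. The gap should be closed before the final analysis.

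**What to change.** Leave the interim stop unchanged. In SAP 6.2, Definition of MTD, replace the sentence on early stopping for toxicity with:

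> At the final analysis, P(DLT rate at dose 1 > 0.48) is recomputed on completed DLT windows for all enrolled patients, whether or not the trial stopped early. If it exceeds 0.7, the MTD is reported as below dose 1 and no RPTD is established. If the trial stopped early and it does not exceed 0.7, the MTD is reported as not determined and no RPTD is established.

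Add the same exception to the MTD definitions in SAP 6.1 and Protocol 17.5, so that the three places agree.

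**Cost.** The data and code will already exist, so the analysis itself is one model run. There are three real downsides:
- Fewer firm statements of below dose 1 after an early stop, also when dose 1 is truly too toxic. At a true rate of 0.60 the simulated share fell from 61–89% to 54–67% across the assumed priors (standard weights).
- Some completed trials with dose 1 truly on target would report no RPTD: 3 to 6% of non-stopped trials at a true rate of 0.48.
- The Appendix 1 simulations should be re-run with the final-analysis rule included, using the likelihood that the trial code actually applies.

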6.3 Missing Data

Primary outcome

The trials team will be informed within 24 hrs if a DLT has been identified. Furthermore a dedicated CRF has been designed which captures only the data required for dose-escalation decisions including key treatment compliance data.

Secondary and tertiary outcomes

Every effort will be made for complete collection and recording of data. Any missing scans or missing blood sample collection will be presented with reasons for missingness. The number of available outcome measures for each secondary and tertiary endpoint i.e. TBRvolume values from the FMISO PET-CT scan, miR-210/PK atovaquone values from blood samples and the number of patients with treatment response from the 3 months post-CRT CT/PET-CT scan will be presented.

No data imputation is planned.

6.4 Sensitivity Analysis

Sensitivity analysis on the primary outcome will be carried out:

• On the sensitivity population defined in Section 4.2 at each interim analysis and for the final analysis

 On the primary analysis population but with a toxic scenario, i.e. assuming patients that currently have insufficient follow-up have a DLT, at each interim analysis

The model and analysis method remain the same as described for the primary analysis.

6.5 Pre-specified Subgroup Analysis

No subgroup analyses are planned.

6.6 Supplementary/ Additional Analyses and Outcomes

There are no supplementary or additional analyses planned.

6.7 Harms

This analysis will be based on the primary analysis population and will be presented as given in Appendix 3.

6.8 Health Economics and Cost Effectiveness (where applicable)

There is no health economics and cost effectiveness analysis.

6.9 Meta-analyses (if applicable)

No meta-analysis is planned

7. VALIDATION OF THE PRIMARY ANALYSIS

Before the trial starts, code for generating dose decisions will be validated by creating a large dataset, and comparing results from analysis using standard logistic regression with the trial code. Although results will not be identical due to the differences between frequentist and Bayesian analyses, with fairly vague priors and a large dataset parameter estimates should be similar. Validation will be stored in the statistical eTMF.

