17.4 Sample size

The sample size will be 20 evaluable patients.

The estimated accrual for this study is one patient per month and therefore the maximum patient accrual is expected to be completed within 20 months. Additional time is required to allow safety data collection to be collected to ensure all patients complete the DLT assessment window.

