3. STUDY METHODS

3.1 Trial Design/framework

Arcadian is a single arm, open-label phase I dose escalation trial using the Time-To-Event Continual Reassessment Method (TiTE-CRM) i.e. a model-based approach to determine the maximum tolerated dose (MTD) of atovaquone in combination with concurrent CRT in patients with NSCLC.

Patients will receive an oral suspension of atovaquone twice daily. The four atovaquone dose levels to be assessed in the TiTE-CRM is as follows:

Dose level	
1	450 mg
2	600 mg
3	675 mg
4	750 mg

Patients will receive atovaquone alone for 1 to 3 weeks during a run-in period followed by 6.5 weeks of concurrent chemoradiotherapy (CRT). The 6.5 weeks of CRT consists of two cycles: Cisplatin ($80 \text{ mg/m}^2 \text{ IV}$)

on days 1 & 22, Vinorelbine (15 mg/m² IV) on days 1, 8, 22 & 29 and thoracic radiotherapy: 66 Gy in 33 fractions, once daily, 5 days a week (Monday-Friday). Therefore, the total treatment duration is expected to be up to 9.5 weeks.

Patients will have follow-up visits at approximately 1, 3 and 6 months after completion of CRT.

The TiTE-CRM will take into account toxicity from the start of the atovaquone run-in period to 12 weeks (84 days) after completion of CRT, so the end of the toxicity assessment period will be approximately the time of the 3 months post-CRT visit.

The figure below shows the study schema

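### The only code validation described in SAP 7 does not exercise partial-follow-up weights or small samples, so dose-decision code that ignored the weights would pass it

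*SAP*

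**What the plan says.** SAP 7 describes a single check of the dose-decision code, to be made on a large constructed dataset ahead of the start of the trial. It consists of "comparing results from analysis using standard logistic regression with the trial code". The section allows for the difference between frequentist and Bayesian results but expects that "with fairly vague priors and a large dataset parameter estimates should be similar". It gives no tolerance. It does not mention weights, partial follow-up, small datasets, the recommended dose, the escalation criteria or the stopping probability.

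SAP 6.2 makes the weights central. A patient without a DLT who has not finished the window is "weighted proportionally to the observed portion of their time window, and treating them as not experiencing a dose limiting toxicity". The weight is min(1, u/T), where u is time followed and T is "pre-specified run-in time + 45 days + 84 days". SAP 3.1 gives the run-in: "Patients will receive atovaquone alone for 1 to 3 weeks during a run-in period". The model is refitted at each new enrolment (SAP 3.4). Protocol 17.4 adds: "The estimated accrual for this study is one patient per month". Protocol 17.2 says the priors were tuned so that early recommendations are sensible. Their values are in SAP Appendix 1, a separate document not available here.

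**The concern.** A validation test should fail when the code is wrong in a way that matters. Standard logistic regression treats every patient without a DLT as a complete non-event. Correct TiTE-CRM code agrees with it only if all weights equal 1, because that is where the two models coincide. A large dataset also swamps the prior. What SAP 7 tests is therefore the dose-toxicity regression with complete data and a negligible prior. Actual decisions rest on few patients, several partly observed, with a prior that counts.

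An error confined to partial weights, or a mis-entered prior, could pass and then affect the recommended dose and the probability used for the safety stop. Ignoring the weights counts a patient followed for one month as a complete non-event, which lowers the estimated DLT rate. That is the unsafe direction.

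**Working it through.** The plan gives no figure to reproduce here, so I emulated the SAP 7 test and then tried small datasets.

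**Model and assumptions.** logit(θ) = log α + β·log(x), with x = 1 to 4 (SAP 6.2). Priors are assumed: log α ~ N(m1, s1) and log β ~ N(m2, s2), with s as standard deviations, written (m1, s1; m2, s2). Under standard TiTE weighting, a DLT contributes θ and a patient without a DLT contributes 1 − wθ. If weights are ignored, the latter becomes 1 − θ. SAP 6.2 prints (1 − θ)·w. Taken literally, w is then a constant that cancels, giving the same posterior as no weights.

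**Step 1: the SAP 7 test, 10,000 simulated patients, all weights 1** (true intercept −0.847, slope 0.600).
- Logistic regression: −0.854 and 0.613 (SE 0.039 and 0.040).
- Standard TiTE, weights ignored, and the likelihood as printed: all −0.853 and 0.612. All three pass.
- Two deliberately different priors, (−2.2, 1; −1, 0.7) and (0.41, 1; 1, 0.5): −0.852 and 0.609; −0.863 and 0.624. The shifts are at most 0.010 and 0.012, below one SE, so a mis-coded prior also passes.

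**Step 2: could the large dataset contain partial follow-up?** With uniform DLT times and weights from 0.1 to 1, standard logistic regression gave −1.589 and 0.489. The implied dose-1 rate is 1/(1 + e^1.589) = 0.17, against a true 1/(1 + e^0.847) = 0.30. Code that handles the weights correctly should not match that, so the expectation of similar estimates makes sense only with all weights at 1.

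**Step 3: how many patients are partly observed?** T runs from 7 + 45 + 84 = 136 to 21 + 45 + 84 = 150 days. With even accrual every 30.4 days, earlier patients are at days 30.4, 60.8, 91.2, 121.6 and 152. The fifth is outside even the longest window. So 2 are inside at patient 3, 3 at patient 4, and at most 4 from patient 5 on. These are upper bounds, because a patient with a DLT counts fully.

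**Step 4: the stopping probability.** Five patients at dose 1, two with DLTs and three without. With T = 143 (14-day run-in), weights are 30.4/143 = 0.21, 60.8/143 = 0.43 and 91.2/143 = 0.64. At dose 1 the slope drops out, because log(1) = 0. The posterior of log α is proportional to prior × θ²(1 − 0.64θ)(1 − 0.43θ)(1 − 0.21θ), or prior × θ²(1 − θ)³ if weights are ignored. P(θ > 0.48) is the part above log(0.48/0.52) = −0.080, by numerical integration (a coarse grid moves results by about 0.01).

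| Assumed prior | P with weights | P, weights ignored | Stop at > 0.7 |
|---|---|---|---|
| (−0.85, 2; 0, 1) | 0.72 | 0.30 | yes / no |
| (−1.10, 1; 0, 0.5) | 0.38 | 0.16 | no / no |
| (−0.08, 2; 0, 1) | 0.80 | 0.36 | yes / no |
| (−1, 1.5; 0, 1) | 0.61 | 0.25 | no / no |

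**Step 5: the recommended dose.** Add one completed patient without a DLT at dose 1, making six. Under the first prior, posterior means at doses 1 and 2 are 0.484 and 0.664 with weights, and 0.332 and 0.535 without. The dose closest to 0.48 moves from 1 to 2, before the escalation criteria are applied. The same move occurs under the third and fourth priors. Under the second, dose 2 is chosen either way. With no DLTs at all (two completed at dose 1, four partial at dose 2), the choice was the same with and without weights under the first three priors.

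**The case against.** **Complete follow-up is inferred.** SAP 7 does not say that the dataset is fully observed. The inference rests on the comparator and the expected agreement, and Step 2 supports it. It remains an inference.

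**Some weight errors could show.** A missing cap at 1 when follow-up exceeds the window would affect completed patients and might surface. A reader might infer that no weight error can be detected. That goes too far: the gap concerns errors confined to weights below 1.

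**Other material may cover the gap.** Protocol 17.3 reports 1000 simulations per scenario. If they used the trial code, they exercised weights, priors and small samples. The documents describe them as design assessment and do not say which code was used. The validation record, held in the statistical eTMF, may also contain more than SAP 7 describes.

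**The consequence is limited.** The TMG reviews each recommendation, and SAP 6.2 frames early stopping as a recommendation to it. A reader might infer that the code alone sets the dose and the stop; it does not. SAP 6.4 also runs a toxic scenario at each interim, counting patients with insufficient follow-up as DLTs, which offers a pessimistic bound. It does not test the weights of those patients, because a DLT has weight 1. The hand check in SAP 5.6 is optional and covers derived variables.

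**The size is conditional.** Steps 4 and 5 use assumed priors and the extreme error of no weighting. In a small simulation (60 trials per cell, four assumed priors, simplified escalation rules), that error changed the stop decision at 0 to 11% of interims, and at 0 to 1% under two priors.

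These points narrow the claim and moderate its size. None is described as validation of the weighted code, so the gap in SAP 7 stands.

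**Conclusion.** The point holds in this form: the one validation that SAP 7 describes does not test weights below 1, the prior, small-sample behaviour, the escalation rules or the 0.7 stopping probability. Code that ignored partial weights would pass. Up to four earlier patients are partly observed at a decision. In the worked cases, ignoring the weights missed the stop under two of four assumed priors and changed the model's dose under three of four.

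The blindness of the test to partial weights follows from the comparator and does not depend on the priors. The sizes do depend on them, and on even monthly accrual.

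A reader might infer that the trial's code is faulty or untested, particularly since the likelihood printed in SAP 6.2 lets the weights cancel. The documents do not support that. The code is not available, the printed form may be a typographical slip, and SAP 6.2 clearly intends partial weighting. This is a weakness in the described validation that should be corrected, not evidence of a wrong dose decision.

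**What to change.** Add a second comparison to SAP 7, between the trial code and an independent calculation of the same weighted TiTE posterior, such as a short two-parameter numerical integration.
- Use small datasets of 2 to 8 patients, with weights between 0 and 1 and the trial's actual priors.
- Match, to a stated tolerance, the four posterior means, P(dose-1 rate > 0.48), and the recommended dose after the no-skipping and escalation rules.
- Check that changing one weight changes the posterior. This fails at once if the weights do nothing.

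The existing large-dataset check can stay as a test of the regression itself. Complete the addition before the code is used for a dose decision. The documents do not say whether decisions have been made; if they have, re-run each once with the validated code. The cost is a small amount of programming and an updated validation record, with no change to data collection.
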